1.2 SCHEDULE OF ACTIVITIES (SOA)

Procedures	Screening and randomization Days -1-5	Enrollment/Baseline Days 2-5 till discharge from NSCU	Step down unit Neurosurgical floor	Final Study discharge
Informed consent	Х			
Demographics	х			
Medical history	Х			
Administer study intervention		Х	x	
Concomitant medication review	х	Х	х	x
Physical exam (including height and weight)	х	Х	x	х
Vital signs (temperature, BP, HR, Oxygen saturation)	х	Hourly and as needed	x	х
Height	Х			
Weight	Х	Х		Х
Performance status	Х	Х	x	Х
Hematology	Х	Х	x	
serum chemistry	Х	Х	X	
Pregnancy test	Х			
EKG (as indicated)	Х	х	As needed	
Daily narcotic use	х	х	x	
Adverse event review and evaluation	х	х	x	x
Radiologic/Imaging assessment (CT, MRI, CTA/CTP, angiogram)	х	х	x	x
Patient satisfaction assessment				x
Complete Case Report Forms (CRFs)	х	х	x	Х

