- Rate of side effects:
 - o presence of intolerable pain at the stimulation site,
 - o skin irritation,
 - o nasopharyngitis,
 - o hoarseness,
 - o dysgeusia,
 - o shortness of breath,

Outcome measures

Primary efficacy variable:

The daily morphine equivalency dosage by visit

Secondary efficacy variables:

- total overall morphine equivalence dosage
- mean daily headache intensity during by visit
- cytokines levels
- blood brain permeability markers in the blood and/or CSF before and after stimulation
- blood brain barrier integrity

Exploratory variables:

(Stroke, vasospasm, DCI, seizure, and central fever)

- The presence of DCI,
- Transcranial doppler velocity,
- The number of days with central fever,
- Incidence of seizures)
- severity of cerebral vasospasm during DSA

Safety variables:

Opiate related adverse events

- urinary retention,
- constipation,
- sedation,
- nausea,
- vomiting and
- pruritis
- Occurrence of Adverse Events (AEs)/Serious Adverse Events (SAEs)

Rate of side effects: presence of intolerable pain at the stimulation site,

- skin irritation,
- nasopharyngitis,
- hoarseness,
- dysgeusia,

- shortness of breath,
- Vital Signs (weight, BMI, SBP, DBP, and pulse rate are collected at each day)

Statistical considerations

Sample size determination

There are no statistical hypotheses in this study, and therefore there is no sample size justification for this study. This is a feasibility pilot study that will allow us to better calculate the sample size for a large, randomized control study comparing VNS to sham device.

General approach:

- Baseline is defined as the value measured at visit 1 (Day 1). Endpoint is defined as last observed value during visit 14 (Day 14).
- Missing efficacy. Two statistical approaches to handling missing data will be performed in this study.
 - The primary analysis will be a repeated measures analysis of the primary efficacy endpoint. Estimates have been shown to be unbiased when the missing data are missing completely at random and when there is ignorable nonrandom missing data.
 - A secondary analysis will utilize an LOCF analysis
- All statistical tests for treatment difference will be 2-sided and conducted at the 0.05 level of significance.

Analysis populations

The following analysis sets will be used for the statistical analysis and presentation of data:

- ITT: All randomized participants will be included in the Intent To Treat (ITT) population.

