The primary efficacy variable, the daily morphine equivalency dose by visit, will be analyzed using a restricted maximum likelihood (REML)-based repeated measures approach (Mixed Model Repeated Measures (MMRM)). The model for analysis will include fixed, categorical effects of treatment, visit, and treatment by visit interaction, as well as the continuous, fixed covariates of baseline value. An unstructured (co)variance structure will be used to model the within-patient errors. If this analysis fails to converge, compound symmetry will be tested. The (co)variance structure converging to the best fit, as determined by Akaike's information criterion will be used as the primary analysis. The Kenward-Roger approximation will be used to estimate denominator degrees of freedom. The primary treatment comparison will be the contrast between treatments at Day 14 for active treatment versus sham treatment. Treatment group differences contrasts will be computed overall and for each analysis visit (i.e., Day 1, Day 2, Day 3, ..., Day 14) and displayed with the respective 95% CIs. Significance tests will be based on least-squares means and Type III sum-of-squares, using two-sided tests at the 0.05 level (two-sided 95% confidence intervals). No imputed values will be used for the MMRM analysis.

Sensitivity analysis

All analyses on the primary efficacy endpoint will be repeated on the PPS

Additionally, the missing data for the mean daily morphine equivalency dose will be computed using an LOCF algorithm and analyzed using the MMREM model.

Analysis of Secondary and Exploratory Variables

For each of the variables mentioned above, the randomization group difference will be examined using a T-test for continuous variables, and Fisher's exact test for categorical variables at each visit.

Analysis of safety variables

Treatment group differences in the occurrence of serious adverse events will be evaluated using Fisher's exact test.

Adverse events:

The primary safety endpoint of this study is the overall incidence of device related serious AEs. AEs and SAEs will be summarized and presented as proportions and respective 95% exact binomial confidence intervals (CIs).

Frequency and percentage of subjects experiencing a specific adverse event will be tabulated by system organ class, preferred term, and treatment group.

Summary tables and subject data listings will be provided.

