- Rate of Symptomatic bradycardia defined as a drop in HR to less than 60 beats per minutes with symptoms, not due to nimodipine. The timing of nimodipine relative to the VNS will be recorded. All patients are on telemetry during the stimulation.
- Rate of drop in blood pressure, defined as a drop in blood pressure requiring fluid resuscitation or vasopressor support thought to be due to the device.
- Rate of side effects:
 - presence of intolerable pain at the stimulation site,
 - o skin irritation,
 - o nasopharyngitis,
 - o hoarseness,
 - o dysgeusia,
 - o shortness of breath,
 - o chest pain,
 - o nausea and vomiting.

Vital signs and weight over time:

Weight, BMI, pulse rate, systolic and diastolic blood pressure will be summarized together with the respective changes from baseline to all study visits.

Laboratory tests over time:

Hematology and biochemistry values will be summarized by treatment group and by visit together with the respective changes from baseline to all study visits.

Procedure	Screening and randomization	enrollment/Baseline Days 2-5 till discharge from NSCU	Step down unit Neurosurgical floor	Final Study discharge
Demographics	х			
Medical history	Х			
Physical exam (including height and weight)	Х	x	Х	х
Vital signs (temperature, BP, HR, Oxygen saturation	Х	hourly or as needed	X	х
Performance status	Х	Х	Х	Х
Hematology, serum chemistry	Х	Х	Х	
Daily narcotic use	Х	Х	Х	
Adverse events	Х	Х	Х	х
Radiologic/Imaging assessment (CT, MRI, CTA/CTP, angiogram)	Х	Х	Х	х
Patient satisfaction assessment				X
EKG (as indicated)	Х	X	As needed	
Concomitant medication review	X	X	х	X

During the ICU length of stay, the following will be assessed and recorded per standard of care:

- Transcranial dopplers (TCD)
- Neuroimaging (CT head, MRI brain, angiograms, CT perfusion with permeability study)
- EVD weaning and day of start of weaning
- Presence of vasospasm delayed cerebral ischemia, Central fever, Cerebral salt wasting.

These are usually recorded in the medical record.

- Urinary retention documented as frequent straight catheterization for more than 3 days
- Constipation evaluated by the need for enema, suppository, lactulose or magnesium

oxide administered

- Blood tests, CSF studies
- EEG results
- Neurologic examination including Glasgow coma score, and NIHSS
- Delirium score

Table 2: Hunt-Hess Score in aneurysmal SAH: (26, 27)

1. Asymptomatic, mild headache, slight nuchal rigidity

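### The SAP uses the Day 1 opioid dose as both baseline covariate and outcome without placing Day 1 before the first stimulation; if stimulation has begun by then, part of the device effect is adjusted away

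*SAP*

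**What the plan says.** In its General approach the SAP writes "Baseline is defined as the value measured at visit 1 (Day 1", with no clock time and no link to the first stimulation. Its Efficacy Analysis section puts this value into the primary MMRM for daily morphine-equivalent dose, "as well as the continuous, fixed covariates of baseline value". The same section asks for treatment differences overall and "for each analysis visit (i.e., Day 1, Day 2, Day 3, ..., Day 14". Day 1 therefore stands on both sides of the model. The headline test comes later: "The primary treatment comparison will be the contrast between treatments at Day 14 for active treatment versus sham treatment". The per-protocol repeat and the LOCF sensitivity analysis use the same model. The primary model in protocol section 9.4.2 has treatment group and time but no baseline covariate, so the SAP alone introduces the adjustment.

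An earlier opioid measurement is planned. Both schedules mark "Daily narcotic use" in the screening column. In protocol section 1.2, stimulation is first marked in the next column, "Enrollment/Baseline Days 2-5 till discharge from NSCU". The SAP's schedule has the same column but no row for stimulation.

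**The concern.** A baseline covariate is safe to adjust for because treatment cannot have changed it. A dose totalled over a day that already contains stimulation sessions lacks that protection. If the device lowers opioid use on that day, patients matched on Day 1 dose are matched on part of the treatment effect, and the later contrasts shrink.

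Early action is plausible on the protocol's own rationale. Section 6.1 describes a device cleared for acute migraine, and section 4.1 has pain rated before and after stimulation. Section 4.4 schedules four sessions a day.

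Protocol section 9.2 and the SAP give the trial's purpose as informing the sample size of a larger trial. An attenuated estimate would carry into that calculation, and no planned sensitivity analysis would reveal it.

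**Working it through.** **1. Where Day 1 falls.** The documents give several origins for the day count:
- The protocol schedule (1.2) and the SAP schedule label the enrolment/baseline column Days 2-5. The protocol's screening column is Days -1-5, so the two windows overlap.
- The figure in protocol 8.2 puts screening on Days 1-3 and baseline with intervention from Days 2-4. It ends at hospital discharge or day 10 counted from the bleed.
- The synopsis starts the study period 24 hours after aneurysm treatment.
- Section 4.1 enrols between days 1 and 5 of aneurysm treatment.

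On the schedule numbering, Day 1 can precede stimulation. Counted from first stimulation, it is treated. Counted from aneurysm treatment, it may be treated for early enrolees and untreated for later ones. None of these sections ties the SAP's Day 1 to the first session.

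**2. Size of the bias if Day 1 is treated.** The documents give no effect size, SD or power, so there is no figure to reproduce. For a later-day device effect d_later:

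adjusted later contrast = d_later − b × d1; share lost = b × (d1 / d_later).

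Assumed, not in the documents: SD = 1, d_later = 0.8 SD, b from 0.3 to 0.7, and d1 between none and all of d_later.

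| Slope b | d1 = 0 | d1 = 0.4 (half) | d1 = 0.8 (equal) |
|---|---|---|---|
| 0.3 | 0.80 (0% lost) | 0.80 − 0.3×0.4 = 0.68 (15%) | 0.80 − 0.3×0.8 = 0.56 (30%) |
| 0.5 | 0.80 (0%) | 0.80 − 0.5×0.4 = 0.60 (25%) | 0.80 − 0.5×0.8 = 0.40 (50%) |
| 0.7 | 0.80 (0%) | 0.80 − 0.7×0.4 = 0.52 (35%) | 0.80 − 0.7×0.8 = 0.24 (70%) |

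A simulated ANCOVA (20 per arm, 5,000 trials per setting) gave 0.69, 0.60 and 0.52 in the middle column. Adjusting for a pre-treatment dose instead returned 0.79 to 0.81 throughout.

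**3. Why power cannot be fixed.** Take a two-sided test at 0.05, the normal approximation, 20 per arm, correlation 0.5 and a Day 1 effect half the later one. The SD after adjusting for Day 1 is √(1 − 0.5²) = 0.866.
- Day 1 covariate: 0.60 / (0.866 × √(2/20)) = 2.19, power 0.59.
- Pre-treatment covariate that predicts equally well: 0.80 / (0.866 × √(2/20)) = 2.92, power 0.83.
- Pre-treatment covariate that predicts nothing: 0.80 / √(2/20) = 2.53, power 0.72.

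If the Day 1 effect is only a quarter of the later one, the Day 1 covariate gives 0.70 / (0.866 × √(2/20)) = 2.56, power 0.72. That equals the power with an uninformative pre-treatment dose. Removing the bias is certain; the gain in power depends on quantities that the documents do not give.

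**4. Day 1 as covariate and response together.** This problem exists wherever Day 1 falls. The SAP says "An unstructured (co)variance structure will be used to model the within-patient errors". With a common slope b, the Day 1 residual is (1 − b) times the Day 1 deviation, so its variance can be driven to zero by letting b approach 1. In one simulated data set the profile log-likelihood was 61 at b = 0.5, 218 at 0.99 and 586 at 0.999999, rising without bound. In the limit the Day 1 contrast is forced to 0 and each later contrast becomes a difference in change from Day 1, which removes all of d1. The fallback to compound symmetry still regresses Day 1 on itself. The table in step 2 therefore describes the model after Day 1 has been dropped as a response.

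**The case against.** A reader might infer that Day 1 must be on treatment because the SAP computes a device contrast there, and conclude that every later contrast is certainly attenuated. The documents do not support that. The contrast shows only that Day 1 is listed as an analysis visit, and the Days 2-5 column and the figure's screening on Days 1-3 both allow an untreated Day 1. Nor do the schedules contradict the SAP by calling the screening dose baseline: they attach that word only to the later column.

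The largest losses are also extreme cases. They need the full effect to be present in the whole Day 1 dose. Section 8.1 takes the first biomarker sample before the 11:30 AM session and section 3 takes it just before the first stimulation. For sampled patients this suggests that a first treated day would include untreated hours and at most three sessions.

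Finally, this is a pilot with no formal hypotheses, and the bias runs towards no effect.

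All of this stands, and it makes the loss conditional. It does not rescue the definition. If Day 1 is untreated, the SAP tests the device on a day when it was not used and may count that day in the overall contrast. For patients who start late, the covariate could also be several days old. The pilot argument lowers the severity only in part, since the SAP still says "All statistical tests for treatment difference will be 2-sided and conducted at the 0.05 level of significance" and the estimate is meant to inform a larger trial.

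**Conclusion.** The concern holds in conditional form. The SAP lets a day of undefined treatment status serve as both the covariate and an outcome in its primary model. If stimulation has begun and the device lowers the Day 1 dose, later contrasts are biased towards no difference by b × d1. That is 15% to 35% of the later effect for assumed slopes of 0.3 to 0.7 and a Day 1 effect half the later one. It is zero if Day 1 is untreated or unaffected. The slopes and the early-effect share are assumptions, and no power loss can be stated from the documents. Severity: should-fix.

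**What to change.** In the SAP's General approach, define baseline as the morphine-equivalent dose in the last 24 hours before randomisation, and in any case before first stimulation. Take it by time stamp from the medication record or from the screening narcotic-use entry. The time stamp is needed because the screening window overlaps the intervention window. Use this value as the MMRM covariate, number analysis days from first stimulation, and include only days after first stimulation as response visits, so that no day is both covariate and outcome. The renumbering must be reconciled with the SAP's Day 14 endpoint and the protocol's stimulation period of up to 10 days.

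The cost is small, because the opioid data are already in the schedule and the electronic record. There are two drawbacks. For early enrolees the 24 hours may overlap the aneurysm procedure, so those patients should be flagged and checked in a sensitivity analysis. The pre-randomisation dose may also predict later doses less well than the Day 1 dose does, which would give up some precision in exchange for removing the bias.

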3 OBJECTIVES AND ENDPOINTS

The primary outcome measurement for effectiveness is:

-The difference between the active and sham treatment groups in mean daily morphine equivalence dosage during study

Secondary endpoints include descriptive comparisons between the active and sham treatment groups in:

- The difference in mean daily headache intensity during the study

The difference between total overall morphine equivalence dosages per subject during study
 Opiate related adverse events (such as urinary retention, constipation, sedation, nausea, vomiting and pruritis)

- The difference in cytokines levels and brain permeability markers in the blood and/or CSF before and after stimulation and between the sham and active device group

- Effects of VNS on brain permeability measured through CT perfusion studies

-The difference in modified rankin scale at hospital discharge and during outpatient follow up. This will be collected retrospectively from the follow up outpatient visit.

Exploratory analyses will include descriptive comparisons of the rates of stroke, vasospasm, DCI, seizure, central fever and severity of vasospasm between the active and sham treatment groups.

OBJECTIVES	ENDPOINTS
Primary Objective:	

Incidence of device related serious adverse events.	Proportion of patients with device related adverse events
The difference between the active and sham treatment groups in mean daily morphine equivalence dosage during study	Morphine equivalence dosage will be calculated per day.
Secondary Objectives	
The difference between the active and sham treatment groups in the mean daily headache intensity during the study	Headache intensity will be measured throughout the day and a mean daily headache intensity will be calculated.
The difference between total overall morphine equivalence dosage between the active and sham group per subject during study	Total morphine equivalence dosage for the duration of the study will be calculated.
Incidence of opiate related adverse events (such as urinary retention, constipation, sedation, respiratory depression, nausea, vomiting and pruritis)	Number of patients with of urinary retention, constipation, sedation, nausea, respiratory depression, vomiting and pruritis.

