9 STATISTICAL CONSIDERATIONS

9.1 STATISTICAL HYPOTHESES

There are no statistical hypotheses in this study. This is a feasibility pilot study that will allow us to better calculate the sample size for a large randomized control study comparing VNS to sham device.

The primary outcome measurements for effectiveness will be:

-The difference between the active and sham treatment groups in mean daily morphine equivalence dosage during the study period

Secondary endpoints include descriptive comparisons between the active and sham treatment groups in:

- The difference between the active and sham treatment groups in mean daily headache intensity during the study period

- The difference between total overall morphine equivalence dosage between the active and sham group per subject during study

-Opiate related adverse events (such as urinary retention, constipation, sedation, nausea, vomiting and pruritis)

Exploratory analyses will include comparisons of the rates of stroke, vasospasm, DCI, seizure, central fever and severity of vasospasm between the active and sham treatment groups.

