Title: Safety and efficacy of non-invasive Vagus Nerve Stimulation (nVNS) in the treatment of headache in Subarachnoid Hemorrhage (SAH)

MAY, 1, 2022

NCT04126408

Overview of study design

This is a single site, randomized, sham-controlled, double-blind study assessing the feasibility, safety, tolerability, and efficacy of non-invasive VNS (nVNS) in the treatment of headache in subarachnoid hemorrhage (SAH).

We hypothesize that two two-minute noninvasive stimulations of the cervical branch of the Vagus nerve, every 5 hours, is efficacious in safely reducing headache intensity and frequency in patients with headache due to SAH, during the patient's intensive care unit (ICU) stay.

After screening and obtaining informed consent, eligible patients diagnosed with SAH on head scans, admitted to the Neurosurgical Intensive Care Unit (NSCU) at Northshore University Hospital will be randomized to either the treatment (stimulation of the cervical branch of the Vagus nerve) or sham (inactive stimulation) group.

Pain intensity will be evaluated every 4 hours. Non-invasive stimulation will be performed every 5 hours.

The treatment arms are the following:

Group 1: Control (patients will receive treatment using an inactive VNS device)

Group 2: Treatment (patients will receive treatment using an active VNS device)

The patients are randomized with equal probability to one of the treatment arms. In total, approximately 40 patients will be recruited

Primary objective

The primary objective of this study is to evaluate the effectiveness of VNS compared to sham device as measured by the mean daily morphine equivalence dosage during the study

Secondary Objectives

The secondary objectives of the study are to compare VNS to sham treatment with respect to effects on the following:

- total overall morphine equivalence dosage
- mean daily headache intensity during the study
- cytokines levels
- blood brain permeability markers in the blood and/or CSF before and after stimulation
- blood brain barrier integrity

Exploratory objectives:

- stroke, vasospasm, DCI, seizure, and central fever
 - The presence of DCI,
 - Transcranial doppler velocity,
 - The number of days with central fever,
 - Incidence of seizures
- severity of cerebral vasospasm during DSA

Safety objectives:

- Opiate related adverse events (such as urinary retention, constipation, sedation, nausea, vomiting and pruritis)
- Occurrence of Adverse Events (AEs)/Serious Adverse Events (SAEs)
- Vital Signs

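### The SAP applies a blanket 0.05 significance rule in a study declared to have no hypotheses, does not label the resulting p-values nominal, and compares serious adverse events between arms only by a Fisher test

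*SAP*

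**What the plan says.** Protocol 9.1 opens with "There are no statistical hypotheses in this study", and 9.2 repeats this as the reason for giving no sample-size justification. Protocol section 3 introduces one list with "Secondary endpoints include descriptive comparisons between the active and sham treatment groups in" and adds: "Exploratory analyses will include descriptive comparisons of the rates of stroke, vasospasm, DCI, seizure, central fever and severity of vasospasm". Protocol 9.4.2 and 9.4.3 use the mixed models to describe differences in dose and headache intensity.

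The SAP agrees under its sample-size heading: "There are no statistical hypotheses in this study, and therefore there is no sample size justification for this study". Its general approach then sets the rule: "All statistical tests for treatment difference will be 2-sided and conducted at the 0.05 level of significance". That rule reaches:

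- **Primary variable.** The SAP names one primary comparison, active against sham at Day 14. It adds: "Treatment group differences contrasts will be computed overall and for each analysis visit", listing Day 1 to Day 14, each with a 95% CI. The analysis is repeated on the per-protocol set and with LOCF.
- **Secondary and exploratory variables.** Each gets a t-test or Fisher's exact test at every visit.
- **Baseline.** Demographics and vital signs are tested between arms in the same way.
- **Safety.** "Treatment group differences in the occurrence of serious adverse events will be evaluated using" Fisher's exact test. AEs and SAEs are also shown as proportions with exact binomial 95% CIs. Device-related SAEs are the primary safety endpoint.

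Neither document contains a multiplicity rule, a testing order, or a statement that p-values are nominal. No between-arm SAE difference with an interval is planned.

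**The concern.** A plan that tests no hypothesis should not attach the same decision threshold to every comparison. Followed as written, the report could present an isolated day, or one exploratory event, as a significant effect. The stated use of this pilot is to size a larger trial, so days or endpoints picked because they crossed 0.05 would carry inflated effects into that calculation.

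The safety side has the opposite weakness. With a small sample, the one planned between-arm statement about SAEs would usually be non-significant even if a real excess existed, and such a result is easily read as reassurance.

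**Working it through.** The documents give no test count, family-wise error rate, effect size, SD, within-patient correlation or SAE rate, so there is no figure of the plan to reproduce. Inputs from the documents are two-sided 0.05, 14 analysis days (SAP) or up to 10 days (protocol), equal allocation, and "In total, approximately 40 patients will be recruited". That gives 20 per arm if nobody is lost, which is an assumption; the mITT set requires at least 7 treated days and can only be smaller.

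**1. Number of tests (inferred).** The SAP lists 5 secondary variables and 5 exploratory items, or 8 if stroke, vasospasm and central fever are counted separately. That makes 10 to 13 variables.

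- Primary variable: 1 overall + 14 daily = 15 contrasts.
- Literal reading, 14 visits: 10 × 14 + 15 = 155, up to 13 × 14 + 15 = 197. With 10 visits: 10 × 10 + 11 = 111, up to 13 × 10 + 11 = 141.
- Restrictive reading, 14 visits: only headache and transcranial Doppler tested daily (2 × 14 = 28); total dose, fever days, DSA severity and barrier integrity once each (4); one cytokine and one marker at four times each (8, assumed); five clinical events once (5). The sum is 45, and 45 + 15 = 60. Counting per-protocol and LOCF repeats with Day 1 left out as baseline, 45 + 3 × 14 = 87. With 10 visits and no repeats: 37 + 11 = 48.

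Baseline and SAE tests come on top.

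**2. Chance results expected under the null.** The expected number is tests × 0.05, whatever the correlation: 60 gives 3.0, 87 gives 4.4 and 155 gives 7.8; the 10-day restrictive count of 48 gives 2.4. Fisher's test rejects less often than 5%. Counting Fisher tests as never rejecting leaves (60 − 5) × 0.05 = 2.8 on the restrictive reading and (155 − 2 × 14) × 0.05 = 6.4 on the literal one. The per-protocol and LOCF repeats largely re-test the same data, so their false positives cluster.

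**3. One outcome tested daily.** This is a simulation of t-tests with no true effect and 20 per arm (20,000 runs). The correlations are assumed. Daily headache intensity, which the SAP tests by t-test at each visit, is the direct example. The chance of at least one p < 0.05 is:

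| Within-patient correlation | 10 days | 14 days |
|---|---|---|
| Constant, 0.9 | 13% | 15% |
| Constant, 0.5 | 29% | 36% |
| AR(1), 0.9 | 19% | 24% |
| AR(1), 0.5 | 36% | 46% |

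Smaller runs differ by about a percentage point.

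**4. SAE comparison at 20 per arm.** For x patients against 0, the two-sided Fisher p is 2 × C(20,x) / C(40,x).

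- x = 4: 2 × 4,845 / 91,390 = 0.106.
- x = 5: 2 × 15,504 / 658,008 = 0.047, the smallest significant split against zero.

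Newcombe 95% interval for 4/20 − 0/20: the Wilson limits are 0.081 to 0.416 and 0 to 0.161. The lower limit is 0.200 − √[(0.200 − 0.081)² + 0.161²] ≈ −0.001. The upper limit is 0.200 + (0.416 − 0.200) = 0.416. The interval runs from about 0 to 42 points.

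Power is the sum of binomial probabilities over all significant tables: 17% for assumed true rates of 20% v 5%, 24% for 30% v 10%, and 19% for 40% v 20%.

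**The case against.** Much can be said for the SAP. It names a single primary contrast, ranks variables as primary, secondary and exploratory, names the mITT set as primary, and files the per-protocol and LOCF repeats as sensitivity analyses. A reader might infer that nothing marks out the comparison of interest, or that the other tests spoil its error rate. Neither follows: the Day 14 contrast keeps its own 5% level. What weakens it as an anchor is that Day 14 lies beyond the protocol's study period of up to 10 days and is not the stated objective, mean daily dose during the study.

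A reader might also infer that SAEs are judged by a p-value alone. They are not. Exact intervals, tabulations and listings are planned, and an unblinded co-investigator reviews aggregate safety data weekly (protocol 10.1.6). The gap is narrower: the only between-arm SAE statement is a test.

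The test count is an inference. Total dose and fever days give one value per patient, biomarkers have a few sampling times, and CT perfusion and DSA occur only in some patients. More than 100 tests requires the literal reading.

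Finally, the protocol is not uniformly descriptive. Section 9.4.3 compares total dose by ANCOVA, 9.1 omits the word for exploratory comparisons, and the synopsis states an efficacy hypothesis. Labelling p-values nominal would therefore settle the conflict with less change than removing them all. That stands and is reflected in the fix.

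**Conclusion.** The concern holds in limited form. The 0.05 rule conflicts with the no-hypotheses statements in both documents, including the SAP's own, and no label tells the reader how to treat the p-values outside the primary contrast. Roughly three or more chance results below 0.05 are expected over the SAP's 14 visits, and somewhat fewer on a restrictive count over 10 days. For one daily outcome, the chance of at least one is about 13% to 36% over 10 days and 15% to 46% over 14, under the assumed correlations and 20 per arm.

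For SAEs, a non-significant Fisher test would say little about safety. It would be tempting to conclude that false reassurance is likely. The documents do not support that: they give no SAE rates, and the planned exact intervals would show the imprecision to anyone who reads them. It is a risk created by the missing difference and interval, and the power figures rest on assumed rates.

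**What to change.** In the SAP's general approach, replace the blanket rule with a statement that results are estimates with 95% CIs, and that any p-value other than the one for the single pre-named primary contrast is nominal and supports no claim. Then:

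- Reconcile the Day 14 contrast with the protocol's up-to-10-day period and its objective of mean daily dose during the study. This may change what is estimated, so it should be decided openly and before unblinding.
- Drop the baseline significance tests.
- Report stroke, DCI, vasospasm and seizure once, as patients with at least one event by arm, instead of testing them at each visit.
- For SAEs and device-related SAEs, give the between-arm risk difference with a 95% score or exact CI, in place of or ahead of the Fisher test, and state that non-significance is not evidence of safety.

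No new data are needed. The cost is a minor revision of SAP wording and tables, and fewer p-values to quote.
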